14.2 Completion of Source Documents and Case Report Forms

The nature and location of all source documents will be identified to ensure that original data required to complete the eCRFs exist and are accessible for verification by the site monitor, and all discrepancies must be appropriately documented via the query resolution process. Study monitors are appointed by the Study Sponsor and are independent of study site staff.

If electronic records are maintained, the method of verification must be determined in advance of starting the study. At a minimum, source documents include the following information for each subject:

- Subject identification (name, sex, race/ethnicity)
- Documentation of subject eligibility
- Date of informed consent
- Dates of visits
- Documentation that protocol specific procedures were performed
- Results of study parameters, as required by the protocol
- IP accountability records
- Documentation of AEs and other safety parameters (if applicable)
- Records regarding medical histories and the use of concomitant therapies prior to and during the study
- Date of study completion and reason for early discontinuation, if applicable

It is required that the author of an entry in the source documents be identifiable. Direct access to source documentation (medical records) must be allowed for the purpose of verifying that the data recorded on the eCRF are consistent with the original source data.

Only designated individuals at the site will complete the eCRFs. The eCRFs must be completed at regular intervals following the clinical study visit schedule. It is expected that all data reported have corresponding entries in the source documents. The Investigator is responsible for reviewing and certifying that the eCRFs are accurate and complete. The only subject identifiers recorded on the eCRFs will be subject number, and subject demographic information.

14.3 Data Review and Clarifications

A targeted review of eCRF data to the subject's source data will be completed by the site monitor to ensure completeness and accuracy. After the eCRFs have been completed, additional data clarifications and/or additions may be needed as a result of the data cleaning process. Data clarifications are documented and are part of each subject's eCRF.

14.4 Sponsor and Monitoring Responsibilities

The Study Sponsor will designate a monitor to conduct the appropriate site visits at the appropriate intervals. The clinical investigation will be monitored to ensure that the rights and well-being of the subjects are protected, the reported data are accurate, complete, and verifiable from the source documents, and the study is conducted in compliance with the current approved protocol (and amendments[s], if applicable), with current GCP, and with applicable regulatory requirements.

All sites must have a site initiation. Prior to screening subjects or performing the informed consent process on any subject, the site must receive a Site Activation Notification from an appropriate Study Sponsor representative. Monitoring will be conducted periodically while the clinical study is ongoing. Monitoring methods may include site visits, telephone, written and fax correspondence. Close-out visits will take place after the last visit of the last subject or after database lock.

A Coordinating Investigator (CI) may be identified by the Study Sponsor. In cases where a CI is required, the Study Sponsor will select the CI based upon their experience, qualifications, active study participation, and their willingness and availability to take on this role. The CI will be bound by confidentiality obligations described in a separate confidentiality agreement between the CI and the Study Sponsor.

14.5 Regulatory Documentation and Records Retention

The Investigator is required to maintain up-to-date, complete regulatory documentation as indicated by the Study Sponsor and the Investigator's files will be reviewed as part of the ongoing study monitoring. Financial information is not subject to regulatory inspection and is to be kept separately.

Additionally, the Investigator must keep study records and source documents until the Study Sponsor provides written approval for their destruction. If the Investigator retires, relocates, or for any other reason withdraws from responsibility of keeping the study records, then the

Study Sponsor must be notified and suitable arrangements made for retention of study records and source documents needed to comply with national and international regulations (generally 2 years after discontinuing clinical development or after the last marketing approval).

14.6 Quality Assurance and Quality Control

The Study Sponsor will secure agreement from all involved parties to ensure direct access to all study related sites, source data and documents, and reports for the purpose of monitoring and auditing by the Study Sponsor, and inspection by domestic and foreign regulatory authorities. Quality control will be applied to each stage of data handling to ensure that all data are reliable and have been processed correctly. Agreements made by the Study Sponsor with the Investigator/Institution and any other parties involved in the clinical study will be provided in writing as part of the protocol or as a separate agreement.

14.7 Publication of the Clinical Trial

Any information other than that which is disclosed upon registration should not be discussed with persons outside the study. The protocol, study data, and information related to the study or to Alcon's products or research programs that is provided by Alcon (Confidential Information) are to be kept confidential, and not disclosed directly or indirectly to any third party other than those involved in the study who has a need to know.

All data and discoveries arising out of the study, patentable or non-patentable, shall be the sole property of Alcon, Inc. Alcon reserves the right of prior review of any publication or presentation of information related to the study. Alcon may use these data now and in the future for presentation or publication at Alcon's discretion or for submission to government regulatory agencies.

The foregoing obligations of confidence and non-use assumed by an Investigator or member of the Investigator's team shall not apply to: (a) information that at the time of disclosure is in the public domain; (b) information that thereafter lawfully becomes part of the public domain other than through disclosure by or through the Investigator or a member of the Investigator's team; (c) information that, as evidenced by an individual's written records, was known to this individual prior to Alcon's disclosure; (d) information that is lawfully disclosed to by a third party not under any obligation of confidence to Alcon; or (e) information that is required to be disclosed by law or government regulatory agency, provided reasonable advance notice of such disclosure is given to Alcon.

In signing this protocol, the Investigator agrees to the release of the data from this study and acknowledges the above confidentiality and publication policy. The provisions of this Statement shall survive the completion of the study.

15 ANALYSIS PLAN

15.1 Subject Evaluability

The final subject evaluability will be determined using the Deviations and Evaluability Plan (DEP) prior to breaking the code for masked treatment assignment and locking the database.

15.2 Analysis Data Sets

The primary analysis set for effectiveness analyses will be the all-implanted analysis set (AAS). AAS includes all randomized eyes with successful IOL implantation.

Additional supportive analyses will be conducted using the best-case analysis set (BAS). BAS includes all eyes successfully implanted that had

- at least 1 postoperative visit
- no preoperative ocular pathology
- no macular degeneration detected at any time
- no previous surgery for the correction of refractive errors
- no major protocol violation

The Safety Analysis Set will include all eyes with attempted IOL implantation (successful or aborted after contact with the eye).

15.3 Demographics and Baseline Characteristics

Summary statistics will be provided for demographic and baseline characteristics by IOL group. Number and percentage will be presented for categorical variables and descriptive statistics including mean, standard deviation (SD), minimum and maximum will be presented for continuous variables.

15.4 Performance Analyses

A success on co-primary effectiveness endpoints would be indicated by successful outcomes on all 4 of these endpoints (2 hypothesis tests and 2 performance targets). A total of 4 hypothesis tests will be conducted to address the primary and secondary effectiveness objectives of the study. Overall Type I error will be maintained at the 5% level using a sequential testing approach.

Hypothesis tests on secondary effectiveness endpoints will be conducted only after successful outcomes on all 4 co-primary effectiveness endpoints are demonstrated.

Analyses on performance targets are based on point estimates.

Only the first eye of each subject will be included in the primary statistical analysis (as described in IS EN ISO 11979-7:2014).

15.4.1 Primary Performance

The co-primary effectiveness endpoints are:

- Monocular distance corrected intermediate visual acuity (DCIVA) at 66 cm
- Monocular best corrected distance visual acuity (BCDVA)
- Monocular depth of focus assessed by the mean defocus curve evaluation
- Percentage of eyes achieving monocular distance corrected intermediate visual acuity (DCIVA) of 0.2 logMAR or better at 66 cm

15.4.1.1 Statistical Hypotheses

The statistical hypotheses in support of the primary effectiveness objectives are:

- ACRYSOF IQ EDF IOL is superior to ACRYSOF IQ Monofocal IOL with respect to mean monocular photopic distance corrected intermediate visual acuity (66 cm from spectacle plane) at Visit 4A (120-180d postoperative)

The null and alternative hypotheses for the first co-primary analysis are:

$$H_0: \mu_{DFT015VA} \geq \mu_{SN60WFVA}$$
$$H_A: \mu_{DFT015VA} < \mu_{SN60WFVA}$$

where $\mu_{DFT015VA}$ and $\mu_{SN60WFVA}$ refer to the mean monocular photopic DCIVA at 66 cm for the test and control lenses, respectively, in the first implanted eye. Second implanted eye analysis will be supportive.

- ACRYSOF IQ EDF IOL is non-inferior compared to ACRYSOF IQ Monofocal IOL with respect to mean monocular photopic best corrected distance visual acuity at Visit 4A (120-180d postoperative). The non-inferiority margin will be 0.1 logMAR.

The null and alternative hypotheses for the second co-primary endpoint are:

$$H_0: \mu_{DFT015VA} - \mu_{SN60WFVA} \geq \Delta$$
$$H_A: \mu_{DFT015VA} - \mu_{SN60WFVA} < \Delta$$

where Δ refers to the non-inferiority margin, set at 0.10 logMAR, and $\mu_{DFT015VA}$ and $\mu_{SN60WFVA}$ refer to the mean monocular photopic BCDVA for the test and control lenses, respectively, in the first implanted eye. Second implanted eye analysis will be supportive.

Two performance targets in support of the primary effectiveness objectives are:

- Monocular mean defocus curve for ACRYSOF IQ EDF IOL has a range of defocus at least 0.5 D greater negative range than ACRYSOF IQ Monofocal IOL at 0.2 logMAR at Visit 4A (120-180d postoperative).
- ACRYSOF IQ EDF IOL has at least 50% of eyes achieving monocular photopic distance corrected intermediate vision of 0.2 logMAR or better at Visit 4A (120-180d postoperative).

15.4.1.2 Analysis Methods

Analysis of the first primary effectiveness endpoint (DCIVA) will be based on a two-sample t-test, with a type I error rate of 2.5%, 1-sided. The difference in means (ACRYSOF IQ EDF IOL minus ACRYSOF IQ Monofocal IOL) and the associated two-sided 95% confidence interval will be presented.

Analysis of the second primary effectiveness endpoint (BCDVA) will be based on a two-sample t-test, with a type I error rate of 5%, 1-sided. The difference in means (ACRYSOF IQ EDF IOL minus ACRYSOF IQ Monofocal IOL) and the associated one-sided 95% upper confidence limit will be presented.

Data poolability will be analyzed by testing a treatment by site interaction effect: first, the interaction effect between treatment and site will be tested using an alpha of 0.15; second, if the interaction effect is found significant, the final analysis model will include site as a random effect.

For the first performance target (depth of focus), the line plot of the average visual acuity at each defocus level (ie, defocus curve) will be used to estimate the negative lens induced depth of focus at 0.2 logMAR. The difference in the depth of focus between ACRYSOF IQ EDF IOL and ACRYSOF IQ Monofocal IOL will be presented. The following sensitivity analyses will be performed on the depth of focus endpoint:

- Exclude extreme outliers (individual depth of focus values less than $Q1 - 3*IQR$ or greater than $Q3 + 3*IQR$)

- Exclude mild outliers (individual depth of focus values less than $Q1 - 1.5 \times IQR$ or greater than $Q3 + 1.5 \times IQR$), where $Q1 = 25$ th percentile, $Q3 = 75$ th percentile, and $IQR = Q3 - Q1$.

The depth of focus data will be presented by IOL group, 3 photopic pupil size ranges [<3.0 mm (small), ≥ 3.0 mm to ≤ 4.0 mm (medium), and >4.0 mm (large)] and three axial length ranges [<21.0 mm (short), ≥ 21.0 mm to ≤ 26.0 mm (medium), and >26.0 mm (long)].

Descriptive summary statistics (number of eyes, mean, median, standard deviation, minimum, and maximum) on individual depth of focus value will be presented by IOL group.

For the second performance target (DCIVA), the percentage of eyes achieving distance corrected intermediate visual acuity of 0.2 logMAR or better in each IOL group will be presented.

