10 SUBJECT POPULATION

The study population consists of male and female subjects 22 years of age and older, with a diagnosis of cataract in both eyes, requiring surgery with implantation of a monofocal IOL in the capsular bag. It is aimed to randomize approximately 220 subjects at approximately 12 US investigative sites. Each site will aim to randomize approximately 20 subjects, and no site will randomize more than 55 subjects (25% of total). Site specific targets may be adjusted based on individual site capabilities. Enrollment projections are as follows:

- 240 subjects to be enrolled/sign consent (approximately 10% screen failure rate is expected)
- 220 subjects to be randomized (approximately 10% discontinuation rate is expected)
- 200 subjects to successfully complete the final study visit (Visit 4A)
 - 100 subjects in the ACRYSOF IQ EDF IOL arm
 - 100 subjects in the ACRYSOF IQ Monofocal IOL arm

Sites must check all entry criteria at Screening/Visit 0 and at both surgical visits (Visit 00, Visit 00A). If a subject is excluded post randomization and prior to first eye surgery (IOL does not come in contact with the eye), the subject should be discontinued from participation in the study. Refer to Section 12.6 Discontinued Subjects for further details.

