11.2 Treatment Assignment / Randomization

Subjects will be randomized in a 1:1 ratio to receive either ACRYSOF IQ EDF IOL or ACRYSOF IQ Monofocal IOL. Randomization will be stratified by site. After signing the ICF, the subject is considered enrolled. After which he/she will be assigned a subject number by the electronic data capture (EDC) system. The Investigator (or delegate) will initiate randomization in EDC:

- after confirming the subject meets eligibility criteria
- post lens power calculation and IOL power selection for both lens types (ie, the power calculation for both the ACRYSOF IQ EDF IOL and the ACRYSOF IQ Monofocal IOL must be conducted prior to randomization)
- within 2 business days of the first eye operative visit (Visit 00)

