15.4.2.2 Analysis Methods

Analysis of first secondary effectiveness endpoint (DCNVA) will be based on a two-sample t-test, with a type I error rate of 2.5%, 1-sided. The difference in means (ACRYSOF IQ EDF IOL minus ACRYSOF IQ Monofocal IOL) and the associated two-sided 95% confidence interval will be presented.

Two performance targets in support of the first secondary effectiveness objective are:

- At least 50% of eyes with ACRYSOF IQ EDF IOL achieve a monocular DCNVA of 0.3 logMAR or better
- The percentage of eyes with DCNVA of 0.3 logMAR or better in ACRYSOF IQ EDF IOL group is at least 25 percentage points higher than in ACRYSOF IQ Monofocal IOL group.

For the first performance target, the percentage of eyes achieving distance corrected near visual acuity of 0.3 logMAR or better in ACRYSOF IQ EDF IOL group will be presented and compared against the performance target of 50%. For the second performance target, the percentage of eyes achieving distance corrected near visual acuity of 0.3 logMAR or better in each IOL group will be presented and the difference between the IOL groups (ACRYSOF IQ EDF IOL – ACRYSOF IQ Monofocal IOL) will be compared against the performance target of 25%.

A success on the first secondary effectiveness endpoint will be indicated by successful outcomes on the hypothesis test and two performance targets. A hypothesis test on the second secondary effectiveness endpoint will be conducted only after successful outcomes on the first secondary endpoint are demonstrated.

For the second secondary effectiveness endpoint, a two-sided 95% confidence interval for the difference in proportions (ACRYSOF IQ EDF IOL – ACRYSOF IQ Monofocal IOL) will be calculated using the Miettinen-Nurminen method (1985), and ACRYSOF IQ EDF IOL will be determined to be superior to ACRYSOF IQ Monofocal IOL if the lower boundary of the confidence interval is greater than zero. This is equivalent to using a type I error rate of 2.5%, 1-sided.

If IOLSAT questionnaire generates scores, the cumulative distribution curves showing the percentage of subjects with a given change in their score compared to baseline by IOL group will be presented to help determine whether any observed differences are meaningful.

In addition, the frequencies of each item in IOLSAT will be summarized by visit with counts and percentages.

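### Site stratifies the randomisation but is left out of the visual-acuity tests, and enters the co-primary model only through an ambiguous, data-dependent switch

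*Protocol*

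**What the plan says.** Section 11.2 of the protocol states: "Randomization will be stratified by site". Section 10 plans the sites: "It is aimed to randomize approximately 220 subjects at approximately 12 US investigative sites", with no site above 25% of the total.

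Section 15.4.1.2 gives both co-primary hypothesis tests as two-sample t-tests without site. For the second it reads: "Analysis of the second primary effectiveness endpoint (BCDVA) will be based on a two-sample t-test", at 5% one-sided. Section 15.4.2.2 does the same for the first secondary endpoint: "Analysis of first secondary effectiveness endpoint (DCNVA) will be based on a two-sample t-test", at 2.5% one-sided.

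Directly after the two co-primary tests, Section 15.4.1.2 adds: "Data poolability will be analyzed by testing a treatment by site interaction effect". The interaction alpha is 0.15, and "if the interaction effect is found significant, the final analysis model will include site as a random effect". The sentence lists no endpoints; from its position it covers DCIVA and BCDVA. Section 15.4.2.2 states no site rule for DCNVA, and the synopsis repeats the t-tests without the switch.

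**The concern.** There are three linked problems.

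1. The factor used to stratify the randomisation is absent from the tests. The t-test remains valid, but it is conservative when site means differ, because its SD contains between-site variation that the stratification has removed from the treatment difference.
2. The final co-primary model is chosen by a test on the same data.
3. Trigger and remedy do not match. The trigger is a lens effect that varies by site; the remedy names only site. A site intercept describes sites with different average acuity, not sites with different lens effects. It tends to narrow the interval just when poolability is in doubt. A random treatment-by-site effect would widen the interval. The protocol does not say which is meant.

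BCDVA non-inferiority is where this can matter. It has the lowest planned power of the two co-primary tests, and Section 15.4 says: "A success on co-primary effectiveness endpoints would be indicated by successful outcomes on all 4 of these endpoints". The secondary tests also wait on it.

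**Working it through.** **Inputs.** From the synopsis (Sample Size Justifications): 100 per arm; BCDVA difference 0.04, SD 0.16, margin 0.10, 5% one-sided; DCIVA and DCNVA difference −0.12, SD 0.18, 2.5% one-sided. From Section 10: about 12 sites. The protocol gives neither the share of variance due to site (ICC) nor the between-site SD of the lens difference (interaction SD). Both are assumptions, shown as ranges.

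**Planned power reproduces.**
- BCDVA: SE = 0.16 × √(2/100) = 0.02263. Power = Φ((0.10 − 0.04)/0.02263 − 1.645) = Φ(1.007) = 84.3% (84.1% with the noncentral t). The protocol states 84%.
- DCIVA and DCNVA: SE = 0.18 × √(2/100) = 0.02546. Power = Φ(0.12/0.02546 − 1.960) = Φ(2.754) = 99.7%. The protocol states above 99%.

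**Effect of omitting site, closed form.** With arms balanced within site and no interaction, the true SE of the difference is 0.02263 × √(1 − ICC), while the t-test still uses about 0.02263. At ICC 0.10 the true SE is 0.02147:
- error of the nominal 5% test: 1 − Φ(1.645/√0.90) = 4.2%;
- power of the t-test: Φ((0.06 − 1.645 × 0.02263)/0.02147) = 85.6%;
- power with site in the model: Φ(0.06/0.02147 − 1.645) = 87.5%.

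Over ICC 0 to 0.20 the t-test's true error runs from 5.0% down to 3.3%.

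**Simulation of the whole rule.** 20,000 trials per setting, N = 200, 12 near-even sites (8 of 17 and 4 of 16 subjects). Non-inferiority is declared when the one-sided 95% upper limit is below 0.10. The site intercept was fitted by REML. The treatment-by-site reading was computed as a t-test on the 12 site differences with 11 df. BCDVA, true difference 0.04, no interaction:

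| Assumed site ICC | 0 | 0.05 | 0.10 | 0.20 |
|---|---|---|---|---|
| Power, t-test (%) | 84.5 | 84.7 | 85.2 | 87.0 |
| Power, treatment plus site (%) | 84.5 | 85.6 | 86.9 | 90.6 |
| Power, protocol rule as site intercept (%) | 84.5 | 84.9 | 85.5 | 87.5 |
| Power, protocol rule with treatment-by-site effect (%) | 81.1 | 81.8 | 82.6 | 84.8 |
| SE relative to t-test when triggered, site intercept | 0.995 | 0.98 | 0.95 | 0.90 |
| SE relative to t-test when triggered, treatment-by-site | 1.31 | 1.28 | 1.25 | 1.18 |
| Readings disagree, % of triggered trials | 22 | 22 | 21 | 17 |

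Always including site gains 0 / 0.9 / 1.7 / 3.6 points. With uneven sites (largest 50 of 200) the gain is 0 / 1.0 / 1.6 / 3.4. The protocol's rule, read as a site intercept, recovers 0.5 points or less.

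**Share of all trials.** With no interaction the switch fires in about 15% of trials per endpoint, so the readings disagree in about 0.15 × 0.22 = 3.3% of all trials at ICC 0 and 0.15 × 0.17 = 2.6% at ICC 0.20. The power gap between the two readings agrees: 84.5 − 81.1 = 3.4 points and 87.5 − 84.8 = 2.7 points.

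**When the lens effect varies by site.** At ICC 0.10, with false non-inferiority judged for a population of sites at a true mean difference of 0.10:

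| Assumed interaction SD | 0.02 | 0.03 | 0.05 | 0.08 |
|---|---|---|---|---|
| Switch fires (%) | 19.5 | 25.1 | 44.2 | 75.4 |
| False non-inferiority, t-test (%) | 4.4 | 5.3 | 7.2 | 11.2 |
| False non-inferiority, treatment plus site (%) | 5.3 | 6.2 | 8.1 | 12.1 |

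At interaction SD 0.05 the protocol rule gives power 81.4% and false non-inferiority 7.5% as a site intercept, against 70.9% and 4.9% with a treatment-by-site effect. The power gap of 10.5 points corresponds to disagreement in about 10% of all trials.

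**The case against.** The strongest reply is that little is broken. The t-test is valid and delivers its stated 84%, and the gain from adding site is zero at ICC 0 and rests on an ICC the protocol does not give. For DCIVA and DCNVA, at 99.7% power, nothing of substance changes. All of that stands: omitting site forgoes efficiency and is not a shortfall against the plan.

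One in five is a rate among triggered trials, and it depends on the planning difference. With no interaction it falls to 7–9% of triggered trials at a true difference of 0.02, and to 1.4–1.9% at zero. Part of it comes from using 11 df: with within-site df and the same SE, the rate at ICC 0 falls from 21% to 15%. The treatment-by-site reading was computed for even sites only. These limits stand too.

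With no interaction, neither reading of the switch inflates error. Under true heterogeneity the unswitched t-test is inflated about as much as the site-intercept reading (7.2% against 7.5% at ICC 0.10 and SD 0.05). The proposed primary model is higher still, at 8.1%. That is a real cost, but only if inference is to a population of sites. The hypotheses in Section 15.4.1.1 "refer to the mean monocular photopic BCDVA for the test and control lenses, respectively, in the first implanted eye" and name no such population. Averaged over the trial's own sites, both tests stay at or below 5.0% (treatment plus site 4.5–5.0%, t-test 3.4–4.2%).

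Finally, a statistical analysis plan, not available here, might name the model terms or a DCNVA site rule. However, Section 15.4.1.2 already fixes the decision rule for the final co-primary model and, as worded, names no interaction term. Clarification elsewhere would still leave that sentence to be corrected.

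**Conclusion.** The concern holds. Site stratifies the randomisation but is missing from three tests, and for the two co-primary tests it enters only through a data-dependent switch whose model is not determined by the text.

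Omitting site costs 0 to 3.6 points of BCDVA power for ICC 0 to 0.20. The switch is the sharper problem. At a true difference of 0.04 its two readings give different BCDVA decisions in 17–25% of triggered trials over interaction SD 0 to 0.05. That is about 3% of all trials with no interaction and about 10% at SD 0.05. Choosing between them after seeing the data would be a discretionary choice on the co-primary test with the least power.

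The size rests on the assumed ICC and interaction SD, near-even sites for the treatment-by-site reading, and the planned difference of 0.04. This should be corrected, but it does not invalidate the planned t-tests.

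**What to change.** In Sections 15.4.1.2 and 15.4.2.2:

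- Prespecify treatment plus site as the primary model for BCDVA, and for DCIVA and DCNVA for consistency. Small sites are pooled by a rule set while masked.
- Delete the model switch. Keep the 0.15 interaction test as a poolability check only.
- If it is significant, report the treatment difference with its interval for each site, and a prespecified sensitivity model with a random treatment-by-site effect. Do not describe the site main effect as handling heterogeneity.
- Section 15.4.2.2 already plans statistics by investigative site and a difference in means with a 95% interval for these endpoints. State that the interval is also given per site.

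This takes a few sentences and no new data. The model uses about 11 of 198 degrees of freedom, with no measurable power loss at ICC 0 (84.5% either way).

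The statistical cost is less conservatism for a population of sites when lens effects vary: about 0 / 0.5 / 0.9 / 1.6–2.3 points more false non-inferiority than the t-test at ICC 0 / 0.05 / 0.10 / 0.20. The sensitivity model is there for this reason. It holds about 5%, but its power is 80–83% at ICC 0–0.10 with no interaction and 70% at ICC 0.10 with interaction SD 0.05, so it is not proposed as primary.

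Per-site intervals are descriptive only. With about 8 eyes per arm the half-width is about 2.145 × 0.16 × √(2/8) = 0.17 logMAR, wider than the margin.
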